## Statistical Analysis Plan

A mixed effects model with random intercepts was run in R (version 4.2.2) using the lme4 package. Given the repeated measures design and the fact that there were incomplete data (i.e., not all subjects were in the OT and placebo condition), the mixed effects model provides a way of examining the effect of condition, controlling for the fact within-subjects nature of the study. For Hypothesis 1, which focuses on the effect of OT vs. placebo, on the condition variable was included in the model. For Hypothesis 2, group (addiction and controls) as well as condition was included. The interaction between group and condition was initially explored. Since there were no significant interaction effects, they were not included in subsequent analyses. P-values from the mixed-effects models were obtained using the Kenward-Roger approximation. Estimated marginal means and their standard errors were obtained from the model results using the R package “modelbased” (<https://cran.r-project.org/web/packages/modelbased/index.html>).

Anatomically-defined regions of interest (ROIs) based on the Harvard-Oxford Atlas were used to extract fMRI BOLD data representing the contrast of Happy own faces vs. Happy unknown faces or Sad own faces vs. Sad unknown faces. The contrasts represent data across all four task runs.

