## Study Protocol

The purpose of this study is to expand upon a previous study of maternal addiction, by conducting a randomized, double-blinded, placebo controlled, crossover study of intranasal oxytocin (OT) on maternal brain responses. 150 mothers from the University of Iowa and the Yale Child Study Center will be enrolled (75 with a history of drug addiction and 75 matched control mothers), along with their 2 to 12-month-old infants, to participate in four study visits over a two-month period.

**Oxytocin administration and neuroimaging procedures.** In this double-blinded placebo-controlled crossover challenge of intranasal OT, maternal brain responses to infant face cues and cries were assessed between participants on receiving either the active (OT) or the inactive (placebo) nasal spray prior to one of two fMRI scanning sessions. Participants, investigators and data analysts were blinded to the identity of the OT and placebo sprays. Infant face images were presented during each scanning session. Specifically, infant face images were presented from each of the four following face conditions: the mother's own infant's face (happy and sad) and an unknown infant's face (happy and sad).

Current smokers were allowed the opportunity to smoke 60 min prior to the scanning session, to avoid any confounding effects of acute nicotine intoxication or withdrawal. All participants will take a urinary pregnancy test prior to the start of the visit. If a mother tested positive, she was excluded from the study due to theoretical concerns about effects of OT and MRI exposure on the pregnancy. The urine sample was used to screen for recent drug use, using the RediCup 5 drug test (for amphetamines, cocaine, marijuana, opioids and benzodiazepines).

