The mothers self-administered a dose of either OT (2 puffs per nostril [6 IU per puff] = 24 IU total) or the placebo spray on each of two fMRI scanning visits, with a randomized order of administration. A stopwatch was started at the moment the participants began intranasal administration, so that the fMRI session began around 50 minutes later. Just prior to drug administration, the mother completed the Positive and Negative Affect Scale (PANAS), to rate her current emotions compared to 40 min later. During the 50-minute delay until scanning, the mother had a breath alcohol and CO (for cigarette usage) test, and completed a series of questionnaires, and demographic information was updated. Fifty minutes after the administration of the nasal spray, the mother participated in the imaging session, passively viewing own and unknown infant faces, and listening to infant cries.

**fMRI parameters.** Using an event-related fMRI design, randomly presented images were viewed for 2 seconds, with a random inter-stimulus interval between 4 and 14 sec. The infant face images were equally divided into 2 affect groups – happy or sad (own-happy [OH], own-sad [OS], unknown-happy [UH], unknown-sad [US]). The intensity of happy and sad affect will be balanced between the “own” and “unknown” faces. Each participant was presented with 4 fMRI runs of 38 different stimulus-trials each (2 catch trials and 6 trials each of OH, OS, UH, US, OC, UC), or 152 trials in all. For the catch trials, participants were asked to press a button when seeing and hearing a bell. The following steps were taken to avoid order-effects. Each run contained all 38 stimulus-trials in a different pseudorandom order that is unique and fixed for that run throughout the study. The order of fMRI runs were randomized (e.g. 1-2-3-4, 2-4-3-1, etc.) in a different sequence for each participant, but consistent across both scanning visits.

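### The Hypothesis 1 oxytocin–placebo estimate is not purely within-mother: one-spray mothers enter through between-mother comparisons, with no group term and no both-scans check

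*Combined protocol and SAP*

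**What the plan says.** The Study Protocol describes a two-visit crossover in which each mother takes oxytocin or placebo "on each of two fMRI scanning visits, with a randomized order of administration". The Statistical Analysis Plan then reports that the data were incomplete: "not all subjects were in the OT and placebo condition), the mixed effects model provides a way of examining the effect of condition". Its answer is a likelihood-based model: "A mixed effects model with random intercepts was run in R (version 4.2.2) using the lme4 package". It describes this model as "controlling for the fact within-subjects nature of the study".

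On fixed effects it says: "For Hypothesis 1, which focuses on the effect of OT vs. placebo, on the condition variable was included in the model". The wording is slightly garbled, but condition is the only term named. Group is named for Hypothesis 2, together with condition.

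The plan does not say how many mothers had one spray only, which spray it was, at which visit, in which group, or why. It states no missing-data assumption and describes no analysis restricted to mothers scanned under both sprays.

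**The concern.** With two scans per mother, a paired difference removes anything stable about the mother: addiction history, smoking, habitual signal level. That is the main attraction of the crossover, and it is what a reader will take from a claim to control for the within-subject design.

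A random intercept does not deliver this for a mother with one scan. Unlike a fixed mother effect, it recovers between-mother information, so her scan is set against other mothers' scans under the other spray. Any systematic difference between one-spray and two-spray mothers can then enter the oxytocin effect, unless it balances across the two sprays. Spray order is randomised, but whether a second usable scan exists is settled later, possibly after dosing, and could differ by spray or group. With condition as the only named term, even a plain group difference is not held constant in the Hypothesis 1 estimate.

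**Working it through.** **Inputs from the documents.** Planned size: "150 mothers from the University of Iowa and the Yale Child Study Center will be enrolled", 75 per group. Two scans per mother, randomised order, random-intercept model, condition only for Hypothesis 1. The plan gives no figure of its own to reproduce here.

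**Assumptions (not in the documents).** 30 or 50 of the 150 mothers have one spray. The within-mother correlation *r* is 0.2 to 0.6. One-spray mothers differ from two-spray mothers by *d* = 0.5 SD. Outcome variance is 1.

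**Formulas.** Let *n* mothers have both scans, *m1* oxytocin only and *m0* placebo only. Generalised least squares under compound symmetry gives, with a = n/(1−r²), b = r·a and D = (a+m1)(a+m0) − b²:

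- variance of the oxytocin–placebo estimate = [2(a−b) + m1 + m0]/D
- bias if all one-spray mothers are shifted by d = d(a−b)(m1−m0)/D
- bias if oxytocin-only mothers are shifted by +d and placebo-only mothers by −d = d[(a−b)(m1+m0) + 2·m1·m0]/D
- both-scans estimate: SE = √(2(1−r)/n), and a stable shift contributes 0

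**Worked case** (n = 120, m1 = 20, m0 = 10, r = 0.4). a = 120/0.84 = 142.86; b = 57.14; D = 162.86 × 152.86 − 57.14² = 21,629. Bias = 0.5 × 85.71 × 10/21,629 = 0.020 SD. SE = √(201.43/21,629) = 0.0965. Bias/SE = 0.21.

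**Bias in SD (in SE):**

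| Both / oxytocin-only / placebo-only | r = 0.2 | r = 0.4 | r = 0.6 |
|---|---|---|---|
| 120/15/15 or 100/25/25, same shift | 0 | 0 | 0 |
| 120/20/10, same shift | 0.026 (0.24) | 0.020 (0.21) | 0.013 (0.17) |
| 100/40/10, same shift | 0.078 (0.67) | 0.059 (0.57) | 0.039 (0.46) |
| 120/15/15, opposite shifts | 0.091 (0.83) | 0.070 (0.72) | 0.048 (0.60) |

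The last row shows that equal counts alone are not enough. The two kinds of one-spray mother must also be alike.

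**Group as the route.** Suppose the groups differ by 0.5 SD and every one-spray mother is in the addiction group.

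- 120/20/10: 45 of the 120 two-spray mothers have an addiction history, so the shift is 0.5 − 0.5 × 45/120 = 0.3125. The bias is 0.3125/0.5 of the table's value: 0.008 to 0.017 SD.
- 100/40/10: 25 of the 100 do, so the shift is 0.5 − 0.125 = 0.375 and the bias is 0.029 to 0.059 SD.

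With group in the model the mean is correctly specified and the bias is 0. The SE rises by less than 1% (largest case 0.1163 to 0.1174).

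**Precision of a both-scans estimate, even splits.** With 30 one-spray mothers the SE goes from 0.110 to 0.115 at r = 0.2, and from 0.080 to 0.082 at r = 0.6. With 50 it goes from 0.115 to 0.126 at r = 0.2, and from 0.085 to 0.089 at r = 0.6. The increase is about 2 to 10%.

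**Simulation** (150 mothers, r = 0.4, true effect 0, 150 replicates, Monte Carlo SE about 0.008):

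| How the second scan is lost | Mixed model | Both scans only |
|---|---|---|
| Tied to a stable trait, equally in both sequences | 0.006 | 0.011 |
| Trait-related, opposite directions by first spray | −0.087 | −0.017 |
| Trait-related, unequal loss rates | −0.033 | −0.004 |
| Depends on the observed first scan, after oxytocin only | 0.009 | 0.071 |

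Neither estimator is safer in every case.

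**The case against.** The strongest reply is that this is a standard and usually appropriate method. A likelihood-based mixed model is valid when loss depends only on observed data, such as the first scan and its spray, and the model is correctly specified. In the last simulation row it is the both-scans estimate that is biased. This stands, and it rules out treating the paired result as the reference or switching to it when the two disagree. With no threshold for disagreement, such a switch would also be a data-dependent choice for each region and contrast.

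A reader might infer that these mothers dropped out after one scan. The documents do not say so. An unusable scan or a missed visit would fit equally well, and the one documented exit is not the mother's decision: after a pregnancy test, "If a mother tested positive, she was excluded from the study".

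The inputs above are also assumed. A 20/10 split raises a two-sided 5% error rate only to about 5.3 to 5.7%. The 40/10 split raises it to about 7.5 to 10.3%, but if loss were unrelated to spray, a split that uneven in either direction would have probability about 0.00002. It therefore presupposes strong spray-related loss, which nothing in the documents suggests.

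Finally, the Hypothesis 2 model already contains condition and group, so a group-adjusted oxytocin estimate exists. That is so, but the plan assigns the oxytocin–placebo question to Hypothesis 1, where group is absent.

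**Conclusion.** The point holds in limited form. The Hypothesis 1 estimate is not purely within-mother, although the plan presents it as controlling for the within-subject design, and nothing described would show whether that matters. Bias needs an uneven split by spray, or selection that differs by spray. A difference between one-spray and two-spray mothers does not produce it alone.

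The actual size cannot be computed, because the counts, split, reasons and within-mother correlation are not given. On the stated assumptions it runs from zero (equal and alike), through about 0.2 SE (20/10), to 0.5 to 0.8 SE in the more extreme cases tabulated. The documents do not support the stronger readings that the estimate is in fact biased or that the mixed model is the wrong primary analysis.

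**What to change.** 1. Add group as a main effect to the Hypothesis 1 model, so that the oxytocin–placebo conclusion comes from the condition-plus-group model. Cost: one degree of freedom and an SE increase below 1% in the cases checked. This removes bias from an additive group difference, but not from differences between one-spray and two-spray mothers within a group.
2. Keep the all-available-data mixed model as primary. Beside it, for each region of interest and contrast, report the estimate from mothers with both scans (paired difference or fixed mother effect), labelled as a sensitivity analysis. Discuss any disagreement and do not change estimator because of it. Cost: one further model run on existing data, with an SE about 2 to 10% larger for the sensitivity estimate under the assumptions above.
3. To make both interpretable, tabulate one-spray mothers by spray received, visit, group and reason. Cost: one table.

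### The OT-versus-placebo models have no scan-visit term in a two-visit crossover with incomplete scans, so a visit shift can bias the estimate or cost power

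*Combined protocol and SAP*

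**What the plan says.** The Study Protocol (oxytocin administration) describes a two-period crossover: mothers took OT or placebo "on each of two fMRI scanning visits, with a randomized order of administration". It gives no allocation ratio or blocking for that order.

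The Statistical Analysis Plan uses a random-intercept mixed model and names its fixed effects:

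- Hypothesis 1: "For Hypothesis 1, which focuses on the effect of OT vs. placebo, on the condition variable was included in the model". The sentence is garbled (possibly *only* was meant), but neither reading brings in visit.
- Hypothesis 2: "For Hypothesis 2, group (addiction and controls) as well as condition was included". A group-by-condition interaction was explored and then dropped.

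The SAP also says that "there were incomplete data (i.e., not all subjects were in the OT and placebo condition", without counts by order or visit. The outcome is "the contrast of Happy own faces vs. Happy unknown faces or Sad own faces vs. Sad unknown faces". No visit, period or sequence term is named anywhere.

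Under fMRI parameters the protocol says "The following steps were taken to avoid order-effects". The steps listed are a trial order for each run "in a different pseudorandom order that is unique and fixed for that run throughout the study", and a run order randomised "in a different sequence for each participant, but consistent across both scanning visits".

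**The concern.** The precautions against order effects work within a scan. They do not separate the first scan from the second. Because each mother's run order is the same at both scans and each run's trial order is fixed, scan 2 repeats the sequence of scan 1. The random intercept removes stable differences between mothers. It does not remove a change within a mother from one visit to the next.

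The outcome gives partial protection, since habituation common to own and unknown faces cancels in the contrast. A shift that differs between the two face types does not cancel. One is possible, because an unknown infant's face is new at the first scan and the mother's own infant's face is not. The documents give no size for such a shift, and do not say whether the same photographs were shown at both scans.

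If there is a shift, one of two things follows:

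1. **Uneven orders, or loss of second scans that differs by order.** OT and placebo then hold different shares of second-scan data, and the condition coefficient takes on part of the shift.
2. **Balanced orders and equal loss.** There is no bias, but the shift sits in the residual. The fitted standard error is too large, the test is conservative, and power falls.

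Without counts by sequence and visit, a reader cannot tell which case applies. A null OT result could partly reflect an inflated standard error.

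**Working it through.** The documents give no SD, correlation, effect size or power calculation, so there is no stated figure to reproduce.

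**Inputs.** From the documents: 150 mothers, two scans, the two stated models. Assumed: outcome SD 1; within-mother correlation 0.5, so within-mother variance σ² = 0.5; visit shift π = -0.5 SD (or -0.3 SD); two-sided 5% level; the order splits and loss rates below; mothers with one scan have the first scan only.

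**Balanced orders, complete pairs.** A mother's OT-minus-placebo difference has error variance 2σ². Without a visit term, the shift enters as +π in one order and -π in the other, so the variance becomes 2σ² + π². The ratio of standard errors is √(1 + π²/(2σ²)).

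- π = -0.5: √(1 + 0.25/1) = 1.118, so the SE is 12% too large.
- π = -0.3: √(1 + 0.09/1) = 1.044, so 4% too large.
- The correct SE is √(1/150) = 0.0816. At π = -0.5 the fitted SE becomes 0.0816 × 1.118 = 0.0913.
- For a true effect of 0.2305 SD, which gives 80% power with visit in the model, power falls to 73% at -0.5 and to 77-78% at -0.3. Type I error falls to 2.7% and 3.9-4.0%. Closed form and simulation agree to this precision.

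**Unequal orders, complete pairs.** With p the share of mothers receiving OT second, bias = (2p - 1)π. An 85/65 split gives 20/150 = 13% of the shift; 90/60 gives 30/150 = 20%.

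**Incomplete scans.** The share of π taken on by the condition coefficient is the condition element of (X'V⁻¹X)⁻¹X'V⁻¹v, where v marks second scans. The table compares this with a REML simulation of the condition-only model (10,000-20,000 trials per scenario). The OT-first group is listed first; reversing the imbalance reverses the sign.

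| Pattern | Bias at -0.5, closed form | Bias at -0.5 (-0.3), simulated | Type I error at -0.5 (-0.3) |
|---|---|---|---|
| 60/75 vs 67/75 complete | -0.021 | -0.019 (-0.012) | 3.4% (4.5%) |
| 45/75 vs 60/75 complete | -0.052 | -0.050 (-0.031) | 5.8% (5.4%) |
| 68/82 split, 80% complete | -0.046 | -0.048 (-0.030) | 5.6% (5.2%) |
| 60/90 split, 60% complete | -0.095 | -0.096 (-0.057) | 12.0% (7.7%) |

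The share of the shift absorbed runs from 0.019/0.5 = 4% to 0.096/0.5 = 19%. With correlation 0.3 and a -0.5 SD shift, the second pattern gives bias -0.042 and type I error 4.8%; the fourth gives -0.094 and 10.5%.

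**How likely the splits are.** Under simple 1:1 randomisation of 150 (an assumption), a split at least as uneven as 68/82 has probability 29%, and 60/90 has 1.8% (two-sided binomial tails).

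**With visit in the model.** Bias is about 0 and type I error about 5% in every pattern.

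**The case against.** The best counter-argument is that randomised order already protects the analysis. If order is drawn by simple 1:1 randomisation and loss of the second scan is unrelated to order, the condition-only estimate is unbiased on average. A simulation on that footing (4,000 runs per cell, -0.5 SD shift) gave mean bias of 0.000, 0.000 and 0.001 at 100%, 80% and 60% completion, with type I error of 4.9%, 5.2% and 5.4%. Missing scans alone do not bias the estimate. Bias needs a realised imbalance or order-related loss, and the documents show no sign of the latter in a blinded study. Some patterns in the table are also unlikely: with 70% completion in both orders, a gap as large as 45/75 vs 60/75 has about a 1% chance. The shift itself is assumed, and novelty may fade within the first scan, since four runs are pooled.

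All of this stands as a limit on the bias claim. It does not remove the point. A reader has one realised trial, with an unreported split. Averaged over simple randomisation, the condition-only standard error is still about 10% larger than with visit (0.091 vs 0.082 with complete data), so precision is lost even where the test is valid.

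Two technical limits also remain. The SAP does not say which scan is missing in mothers with one condition, and the simulation used a t cut-off in place of the Kenward-Roger method.

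**Conclusion.** The concern holds. Neither stated model has a visit term, and the protocol's precautions do not address visit. The harm depends on a visit shift in the own-minus-unknown contrast, which the documents neither establish nor rule out. With no shift, the omission costs nothing.

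With a shift of -0.3 to -0.5 SD and correlation 0.5, the most likely harm is modest: a few points of power (80% to 77% or 73%) under balance, or a bias of a few hundredths of an SD under moderate imbalance. A clear excess of false positives needs an extreme split with heavy loss of second scans. The point should be fixed because the stated model is weaker than the standard crossover model and the correction is nearly free, not because the conclusions are shown to be wrong. Confidence is moderate, as every magnitude rests on assumed inputs.

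**What to change.** Add scanning visit (1 or 2) as a fixed effect in both models:

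- Hypothesis 1: outcome ~ condition + visit + (1 | mother)
- Hypothesis 2: outcome ~ condition + group + visit + (1 | mother)

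Take the estimated marginal means from these models. Report the number of scans analysed by sequence, visit and condition, so that readers can see whether OT and placebo data are balanced over visits.

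The cost is one degree of freedom and a re-run on existing data. With no visit shift, the fitted SE rises by 0% (balanced), 0.5% (45/75 vs 60/75 complete) or 2.0% (60/90 split, 60% complete). With a -0.5 SD shift it falls by about 11% (0.0911 to 0.0814), 9% (0.1025 to 0.0931) and 7% (0.1070 to 0.0993) respectively. A visit term does not deal with carryover, which is a separate question.

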All imaging was performed using a 3 Tesla MRI scanner. Visual images were generated using a computer controlled LCD projector, and presented to the mother via an overhead mirror display. Regional brain activation was assessed by measuring changes in blood-oxygen-level-dependent functional MRI signal (BOLD-fMRI). Participants participated in whole-brain functional runs of around 185 scans each (multiband imaging with a factor of 6; 52 slices; TR 1000 msec; TE 30 msec; flip angle, 65 degrees; 64 x 64 matrix [in plane resolution]; field of view [FOV] 220 mm; slice thickness 2.4 mm; gap thickness 2.4 mm). High-resolution T1-weighted structural images (166 slices, in plane resolution 256 x 256; FOV 245 mm; slice thickness 1 mm) were also acquired. After the scanning session, each mother rated each of the face images on how they thought the infant was feeling, as well as their own feelings of pleasure or arousal, using an adaptation of the Self-Assessment Manikin.

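### The Hypothesis 2 model compares non-randomised groups recruited from two institutions but contains no site term

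*Combined protocol and SAP*

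**What the plan says.** The Study Protocol section states that "150 mothers from the University of Iowa and the Yale Child Study Center will be enrolled", half with a history of addiction and half described as "75 matched control mothers". It does not name the matching variables. Only the order of oxytocin and placebo is randomised; group is a characteristic the mothers bring with them. On equipment it says "All imaging was performed using a 3 Tesla MRI scanner", in the singular, without saying where it stood or whether there was more than one.

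The Statistical Analysis Plan section says that "A mixed effects model with random intercepts was run in R", and for the group comparison: "For Hypothesis 2, group (addiction and controls) as well as condition was included". The group-by-condition term was tried and removed: "Since there were no significant interaction effects, they were not included in subsequent analyses". The outcome for each region of interest is an own-minus-unknown infant face contrast. The section also reports that "there were incomplete data (i.e., not all subjects were in the OT and placebo condition".

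Site, institution and scanner do not appear as a covariate, random effect, stratum or sensitivity analysis. No count of addiction and control mothers by site is given.

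**The concern.** Randomising treatment order within each mother protects the oxytocin-placebo comparison from stable differences between mothers, including differences between sites. The addiction-control comparison has no such protection. It is a between-mother comparison, so whatever separates mothers at the two institutions (population, recruitment route, scanner gain if there were several scanners) enters the group effect in proportion to how unevenly the groups are spread over the sites.

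The grouping factor for the random intercept is not named, but the stated reason is the within-subject design, so it is presumably the mother. Such an intercept models the correlation between a mother's two sessions. It does not take a site difference out of the group contrast.

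Hypothesis 2 is not worded in the documents. Because the interaction was dropped and group kept, the group main effect is the natural target, and the point applies to that reading only. At stake is whether a site difference could be reported as an effect of addiction.

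**Working it through.** The plan states no alpha, SD, effect size, dropout rate or site split, so it has no figure of its own to reproduce. The calculation shows how large the problem could be.

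**Inputs**

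| Input | Value | Source |
|---|---|---|
| Mothers per group, n | 75 | Study Protocol |
| Total SD of one session's contrast within site | 1 (between-mother variance vb = 0.5, residual ve = 0.5, so correlation 0.5) | assumed |
| Share with one session only, f | 0.2 | assumed; the SAP says only that some data are incomplete |
| Site difference, d | 0.3 or 0.5 SD | assumed |
| Share of addiction (p1) and control (p2) mothers at one site | 55/45 to 70/30, mirrored in controls | assumed |
| Test | two-sided 5% | assumed |

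**Step 1: standard error with no site difference.** Information per mother is I = (1−f)/(vb + ve/2) + f/(vb + ve) = 0.8/0.75 + 0.2/1 = 1.267. Then SE0 = √(2/(75 × 1.267)) = 0.1451.

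**Step 2: bias when site is left out.** Bias = d(p1 − p2). For d = 0.5 and 60/40 v 40/60: 0.5 × 0.20 = 0.10 SD. For 70/30 v 30/70: 0.5 × 0.40 = 0.20 SD.

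**Step 3: model standard error when site is left out.** The site difference inflates the apparent between-mother variance to vb + d²[p1(1−p1) + p2(1−p2)]/2. At 60/40 with d = 0.5 this is 0.5 + 0.25 × 0.24 = 0.56, so I = 0.8/0.81 + 0.2/1.06 = 1.176 and SEu = √(2/(75 × 1.176)) = 0.1506.

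**Step 4: type I error with site counts fixed.** P(Z > (1.96·SEu − bias)/SE0) + P(Z < (−1.96·SEu − bias)/SE0). At 60/40 with d = 0.5 the limits are (0.2952 − 0.10)/0.1451 = 1.345 and (−0.2952 − 0.10)/0.1451 = −2.72, giving 9.3%.

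**Step 5: standard error with site in the model.** SE0/√(1 − (p1 − p2)²): 0.1481 at 60/40 and 0.1583 at 70/30.

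| Mix (addiction v control) | d | Bias (SD) | Type I error, no site term | SE without site | SE with site |
|---|---|---|---|---|---|
| 50/50 v 50/50 | 0.5 | 0 | 4.2% | 0.151 | 0.145 |
| 55/45 v 45/55 | 0.3 | 0.03 | 5.2% | 0.147 | 0.146 |
| 55/45 v 45/55 | 0.5 | 0.05 | 5.4% | 0.151 | 0.146 |
| 60/40 v 40/60 | 0.3 | 0.06 | 6.6% | 0.147 | 0.148 |
| 60/40 v 40/60 | 0.5 | 0.10 | 9.3% | 0.151 | 0.148 |
| 70/30 v 30/70 | 0.3 | 0.12 | 12.6% | 0.147 | 0.158 |
| 70/30 v 30/70 | 0.5 | 0.20 | 25.9% | 0.150 | 0.158 |

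With an equal mix and d = 0.5 the SE is 0.1508/0.1451 = 1.04 times as large. An effect with 80% power after adjustment, (1.96 + 0.84) × 0.1451 = 0.406 SD, then has about 77% power.

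**Sensitivity at d = 0.5** (60/40, then 70/30):
- One-session share from 0 to 40%: 9.5% to 9.0%; 27.0% to 24.9%.
- Between-session correlation from 0.3 to 0.7: 9.8% to 8.9%; 28.5% to 23.9%.
- Only 50 v 50 mothers: 7.5%; 18.5%.

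**Check by simulation.** Random-intercept REML fits were run on 8,000 null data sets per case, with d = 0.5, f = 0.2 and a t test on 147 df in place of Kenward-Roger.

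| Mothers at one site, of 75 v 75 | Group, no site term | Group, with site | Oxytocin-placebo | Interaction |
|---|---|---|---|---|
| 45 v 30 | 8.4% | 4.8% | 4.6% | 5.2% |
| 52 v 22 | 25.5% | 4.8% | 4.9% | 5.1% |

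The site term restores the level of the group test. The randomised comparison and the interaction keep theirs without it.

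**The case against.** The strongest reply is that the harm needs several things the documents do not show: both institutions contributed analysed mothers, the group mix differed between them, the face contrast itself differs by site, and Hypothesis 2 is about the group main effect. That is correct, and it is why the size is conditional.

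The controls are described as matched. If site was a matching variable, or controls were recruited locally alongside cases, the mix would be close to equal and a 70/30 reversal implausible. The mild cases then apply: 5.4% at 55/45 with 0.5 SD; on the same formula, 5.9% at 90/10 v 80/20 with 0.5 SD and 5.7% at 60/40 with 0.2 SD. But no matching variable is named, so balance on site cannot be assumed. Even with perfect balance, adding site recovers precision when sites differ.

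The scanner is described in the singular with one set of parameters, which may mean one machine. The own-minus-unknown contrast cancels additive scanner offsets, though not differences in gain. Neither fact removes a difference between the two recruited populations, so the point concerns site, and scanner only if there were several.

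The interaction could instead have been the target of Hypothesis 2, since "The interaction between group and condition was initially explored". On that reading an additive site difference does no harm. Finally, adjustment is not free: at 70/30 it raises the SE. If sites differ because of characteristics tied to addiction, the meaning of the adjusted contrast also needs thought. Both are reasons to show the two estimates together, not to omit the adjusted one.

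**Conclusion.** The concern holds. Two institutions were planned, group is not randomised, and no term in the stated Hypothesis 2 model accounts for site. The omission is plain from the text; its consequence cannot be determined from it. On the assumed inputs, inflation of the group test ranges from negligible, when the site mix is nearly equal or the site difference small, to about 9% at 60/40 v 40/60 and about 26% at 70/30 v 30/70 with a 0.5 SD site difference. These figures rest on assumed values for the SD, correlation, missing sessions, site difference and site split. Confidence that the issue matters in this trial is therefore medium. The point is limited to the addiction-control main effect. The change should be made because it is cheap and either removes possible confounding or recovers precision.

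**What to change.** 1. Tabulate group by site for the mothers actually analysed. If all or nearly all came from one site, say so; no adjustment is then needed.
2. If both sites contributed, add site as a fixed effect to the Hypothesis 2 model. Add scanner as well if there was more than one and it does not coincide with site.
3. The SAP already reports an interaction result, so the analysis appears to have been run. Give the site-adjusted group estimate beside the unadjusted one and label it as added later.
4. As a secondary reporting point, name the variables used for matching.

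The cost is one degree of freedom and one re-run. On the assumptions above, the group SE falls from 0.151 to 0.145 with an equal mix and a 0.5 SD site difference. At 60/40 it falls from 0.151 to 0.148 with 0.5 SD, or rises trivially from 0.147 to 0.148 with 0.3 SD. At 70/30 with 0.5 SD it rises by about 6%, from 0.150 to 0.158, and that is where the bias removed is largest.
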